### **7.3 Follow up**

- 7.3.1.** If discharged from the hospital prior to day 28, patients will followed up with (in clinic or by telephone) through day 28 as outlined in study calendar Section 6.1. Additional visits or telephonic contacts will be obtained as clinically indicated for patients with toxicities deemed to be related to the MSC infusion, which will be followed until resolved.

### **7.4 Drug Toxicity and/or Adverse Reactions**

- 7.4.1.** For consistency, toxicity for all patients will be evaluated using the NCI Common Toxicity Criteria scale (version 5.X; <http://ctep.cancer.gov>).
- 7.4.2.** Adverse events will be collected as per SOP [J02.05.XX](#) and [J02.75.XX](#). Data on all new adverse experiences/toxicities (regardless of seriousness) and worsening of baseline toxicities by at least one grade following infusion will be collected for documentation purposes for 4 weeks after the last dosing of the study drug/biologic with the exception of all toxicities which were deemed to be related to the MSC infusion, which will be followed until resolved.
- 7.4.3.** Serious Adverse event data will be collected and reported as per SOP J02.06.XX until 28 days after the last dosing of study drug/biologic or until time of discharge, whichever comes first, and should consist of both solicited and volunteered events reported by the patient.
- 7.4.4.** Infusion/allergic reactions will be evaluated by continuous monitoring the patient's vital signs from the time of administration until two hours after starting the infusion.
- 7.4.5.** Treatment-related serious adverse events (tSAE) will be considered as those directly related to the investigational infusion product. Adverse event grading

will be as defined by the NCI Common Terminology Criteria for Adverse Events (CTCAE), Version 5. In making this assessment, there should be consideration of the probability of an alternative cause (for example, COVID-19 itself or some other condition preceding randomization) and the timing of the event with respect to study treatment. The safety endpoint of the study is tSAE, defined as:

- Any grade 5 AE
- Any grade 4 AE that fails to return to grade 2 within 72 hours post-infusion
- Grade 2 to 4 allergic reactions (severe rash, bronchospasm, and immediate-type allergic reactions)
- Arterial or venous thromboembolic event occurring within 48 hours of infusion
- Serious Adverse Event (SAE) that, in the treating physicians' judgment, is considered related to MSC infusion and requires withdrawal from the study

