### **1.4 COVID-19-associated coagulopathy (CAC)**

Abnormalities in coagulation parameters have been observed in patients hospitalized with COVID-19 disease [12, 19, 22, 23]. Most common are elevations in fibrinogen and D-dimer, which may correlate with a rise in inflammatory markers. However, some patients with severe COVID-19 disease develop classic disseminated intravascular coagulopathy (DIC) with moderate to severe thrombocytopenia, prolongation of PT/aPTT, elevated D-dimer, and fibrinogen less than 100 mg/dL. Tang et al reported that use of low molecular weight (LMWH) or unfractionated (UFH) heparin was associated with decreased mortality in patients with severe COVID-19 disease [24]. Conversely, progressively increasing D-dimer levels were associated with increased mortality. Based on these (and related) findings, monitoring of platelet counts, PT/aPTT, D-dimer and fibrinogen levels is strongly recommended. While the use of therapeutic anticoagulation in patients with severe COVID-19 disease is still under study, prophylactic low dose heparin anticoagulation is recommended in the absence of active bleeding or other contraindications.

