## **2.3 Study Objective:**

To evaluate the safety and clinical benefits of banked mesenchymal stromal cells (MSCs) versus control for treatment of patients with COVID-19 induced ARDS.

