# - if inadequate response to initial infusion, a second infusion may be given within 3-5 days following the first infusion; no more than 2 infusions will be administered

@ - coagulation studies = PT/aPTT, d-dimer, fibrinogen

& - collected pre-infusion and 3-4 hours post-infusion

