### 8.5 Statistical Analysis

All patients who received any MSC infusions in the MSCs arm or supportive care in the control arm will be included in the safety analyses. All efficacy analysis will be based on the intent to treat (ITT) population, defined as eligible and randomized subjects.

Adverse event data and corresponding toxicity grades after treatment will be summarized descriptively by treatment arms. All adverse events, grades, and attributions

will be listed and tabulated. Toxicity information including the type, severity, time of onset, time of resolution, and the probable association with the study regimen will be tabulated and summarized by treatment arms. Rate of tSAEs in patients treated with MSCs will be reported as proportion and its 95% confidence interval overall and by cancer status (cancer patients versus non-oncologic patients).

Clinical outcome data (increase in oxygen saturation, decrease in oxygen supplementation, progression to mechanical ventilation or ECMO, evolution of other end-organ damage, severity of ARDS, mortality rate, cause of death, duration on ventilation, durations of ICU stay and hospital stay, duration of vasopressor use, negative SARS-Co-V-2 RT-PCR by day 28, and change in disease severity scores and corticosteroid use) will be summarized descriptively. Categorical variables will be summarized by frequencies and percentages. Continuous variables will be summarized by means, standard deviations, medians, interquartile ranges.

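### Safety is framed as MSC versus control, but the primary safety endpoint is MSC-only and Section 7.4 times AE and SAE collection from the last MSC dose, at odds with the study calendar

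*Combined protocol and SAP*

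**What the plan says.** The objective in Section 2.3 is comparative: "To evaluate the safety and clinical benefits of banked mesenchymal stromal cells (MSCs) versus control". The primary hypothesis (2.2.1) and the design statement (8.1) also set safety against the control group.

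The primary safety endpoint is tied to the product. Section 7.4.5 opens: "Treatment-related serious adverse events (tSAE) will be considered as those directly related to the investigational infusion product". Section 8.4 monitors it in the MSC arm, and 8.5 states: "Rate of tSAEs in patients treated with MSCs will be reported as proportion and its 95% confidence interval".

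The collection rules are anchored on dosing:
- **AEs (7.4.2).** Data on new events, and on baseline toxicities that worsen after infusion, "will be collected for documentation purposes for 4 weeks after the last dosing of the study drug/biologic". Toxicities judged related to MSC are followed to resolution.
- **SAEs (7.4.3).** Collection ends 28 days after the last dose, or at discharge if that is earlier.

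Other sections describe a different schedule:
- **Section 7** sets day 0 at randomization for controls and at infusion for the MSC arm, and applies the evaluations to both arms.
- **Section 6.1** has an adverse events row from day 0 to day 28 that is not limited to one arm. The day-28 visit carries a 2-day window, printed as +2. A footnote adds that "a second infusion may be given within 3-5 days following the first infusion".
- **Section 7.3.1** says that after an early discharge "patients will followed up with (in clinic or by telephone) through day 28".
- **Section 8.5** places controls in the safety analysis and tabulates AEs descriptively by arm.

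**The concern.** A comparative safety question needs the same events, counted over the same period, in both arms. Here the primary endpoint cannot supply the comparison, and the supporting AE and SAE rules start and stop on an event that controls never have.

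The issue matters most for thromboembolism. Section 1.4 describes a coagulopathy of COVID-19 itself: "Abnormalities in coagulation parameters have been observed in patients hospitalized with COVID-19 disease". Section 1.6 describes procoagulant potential of MSC preparations, though it calls such complications rare with bone-marrow MSCs. When disease and treatment could both cause the same event, case-by-case attribution in an open-label trial is weak evidence. A concurrent randomized control arm is the better instrument, and the plan already has one of 30 patients. If the two arms are observed over different windows, a by-arm table cannot be read at face value.

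**Working it through.** **1. The plan's own safety figures.** These are the stopping probabilities in 8.4.
- An exact binomial recursion over MSC patients 1 to 30, using the tabulated boundary, gives a stopping probability of 4.9% at a true tSAE rate of 25% (stated 5%) and 81.3% at 50% (stated 81%).
- For the run-in, P(3 or more of 6) at a 10% rate = 1 − (0.9⁶ + 6·0.1·0.9⁵ + 15·0.1²·0.9⁴) = 1 − (0.5314 + 0.3543 + 0.0984) = 1.6%, as stated. At 5% it is 0.2%.

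The figures reproduce. All of them concern MSC patients alone, so none bears on a comparison with control.

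**2. Length of the windows.** The AE window in 7.4.2 ends on day of last dose + 28. Scheduled contact ends on day 28, or day 30 at the latest.

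| Patient | AE end (7.4.2) | SAE end (7.4.3) | Calendar |
|---|---|---|---|
| Control | not stated | not stated | day 28 |
| MSC, one infusion | 0 + 28 = day 28 | day 28 or discharge | day 28 |
| MSC, second infusion day 3 | 3 + 28 = day 31 | day 31 or discharge | day 28 |
| MSC, second infusion day 5 | 5 + 28 = day 33 | day 33 or discharge | day 28 |

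For a re-dosed patient:
- If contact stops at day 28, post-dose observation is 28 − 5 = 23 to 28 − 3 = 25 days of the 28 required. The shortfall is 3/28 = 10.7% to 5/28 = 17.9%.
- If the last visit is on day 30, observation is 25 to 27 days and the shortfall is 1/28 = 3.6% to 3/28 = 10.7%.
- If 7.4.2 is followed in full, the patient is observed for 31 to 33 days against 28 for a control, which is 10.7% to 17.9% longer.

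**3. Origin of the clock.** The delay from randomization to infusion is not given. Assuming 0 to 2 days, MSC windows end between 0 + 0 + 28 = 28 and 2 + 5 + 28 = 35 days after randomization, against 28 for controls. An event in the MSC arm between randomization and infusion falls outside 7.4.2, which starts at infusion.

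**4. What is already compared or summarized.**

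| Outcome | Planned handling |
|---|---|
| Death | day-28 mortality is a secondary endpoint (2.3.2); survival from randomization is compared by log-rank test (8.5) |
| End-organ damage | exploratory endpoint (2.3.3); descriptive summary (8.5) |
| AEs of any type | descriptive tables by arm (8.5) |
| All-cause SAEs | no between-arm estimate |
| Thromboembolism, any attribution | no between-arm estimate |

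**5. Precision of an added estimate.** With 30 per arm and a common rate p, the 95% half-width of the risk difference is 1.96·√(2p(1−p)/30). At an assumed p = 20% this is 1.96·√(0.32/30) = 0.20. At 10% it is 0.15 and at 50% it is 0.25.

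**The case against.** The strongest reply is that the plan does look at controls. Section 7.4.1 grades toxicity in all patients, the calendar's AE row covers both arms, Section 7 gives controls a day 0, and 8.5 tabulates AEs by arm. An infusion-attributed endpoint with single-arm stopping is a normal choice for an early-phase cell therapy trial. Collection detail is also delegated to SOPs that are not part of the document.

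Much of this stands, and it rules out several stronger readings:

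- *A reader might infer that controls have no AE window at all.* The calendar and Section 7 imply randomization to day 28. The defect is that 7.4.2 conflicts with this and that 7.4.3 states no SAE window for controls.
- *A reader might infer that death and organ failure cannot be compared.* They are already summarized or compared, as shown in step 4 of the working.
- *A reader might infer that every re-dosed patient overruns on SAEs.* The discharge cut-off confines that overrun to those still in hospital. The AE overrun applies to all surviving re-dosed patients.
- *A reader might take 18% as an arm-level excess.* It is the upper end for a re-dosed patient, and the proportion re-dosed is not given.
- *A reader might say a control can never meet the tSAE definition.* The opening definition points that way, but the listed component for any grade 5 event carries no attribution wording. Read literally, it could take in a control death. The text is ambiguous.

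Two further concessions are due. Section 7.4.2 applies whatever the seriousness, so a serious event after discharge in an infused patient would still be recorded as an AE, though 7.4.3 would not collect it as an SAE. And two tSAE components are confined to 48 or 72 hours after infusion, so the late tail matters little for those.

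The reply does not remove the conflict. By-arm tables are promised, while the section that governs collection times it from the last MSC dose.

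**Conclusion.** The point holds as an inconsistency with a modest, correctable effect. The stated safety comparison is not answered by the primary safety endpoint. The by-arm AE summaries would rest on unequal windows: 28 days for controls under the calendar, and up to 31-33 days from first infusion for re-dosed patients under 7.4.2, with different origins in the two arms. SAEs have no stated window in controls and stop at discharge in MSC patients. No effect estimate is planned for all-cause SAEs or thromboembolism.

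The window arithmetic rests only on the second-infusion timing and visit schedule in the protocol. The 28-35 day range from randomization rests on an assumed delay of 0-2 days. How much the imbalance would move an event rate cannot be computed, because neither the re-dosing proportion nor the late event rate is given. Nothing here changes the sample size, the power or the tSAE stopping boundary.

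**What to change.** **Sections 7.4.2-7.4.3 and 6.1.** Collect AEs and SAEs in all randomized patients from randomization through 28 days after randomization, regardless of discharge. Use the follow-up contacts already scheduled in 7.3.1, and make the calendar agree. Because MSC day 0 is the infusion, state the randomization origin explicitly and include events before infusion. For the six run-in patients, count from first infusion and report them separately.

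**Section 8.5.** Add a risk difference with 95% CI, 30 v 30 and randomized patients only, for all-cause SAEs, grade 4-5 AEs and arterial or venous thromboembolism over that window, regardless of attribution. Label it as estimation, not a powered test.

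**Re-dosed patients.** Reconcile 7.4 with the day-28 end of follow-up. One way is a single telephone contact 28 days after the second infusion (day 31-33), with later events listed separately and kept out of the between-arm contrast.

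**tSAE.** Keep it for stopping in the MSC arm, and clarify whether the grade 5 component requires attribution. If the sponsor does not want the comparison, the alternative is to restate the safety objective as single-arm.

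**Cost.** Wording in 7.4, 6.1 and 8.5, one extra table, a few telephone contacts, and acceptance of a wide interval.

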### **1.3 ARDS due to COVID-19 Disease**

Angiotensin converting enzyme-2 receptor (ACE-2) has been identified as a primary host receptor for cell entry utilized by SARS-CoV-2 similar to SARS-CoV [15, 16]. ACE-2 is highly expressed in multiple organs including but not limited to the oral cavity, human airway epithelia, myocardial cells, and kidney proximal tubule cells, and high expression may increase susceptibility to viral damage. It has been reported that approximately 50% of patients with COVID-19 pneumonia will progress to ARDS [12, 13, 17], with mortality approaching 50% in various studies [10, 12, 13, 17, 18]. Risk factors for ARDS and increased mortality include age (older than 60 years), presence of comorbidities such as hypertension, diabetes, heart disease, COPD, immunocompromised states, elevated markers of inflammation and higher disease severity as evidenced by high APACHE II, SOFA, and CURB-65 scores [10, 18-21]. At present, no effective antiviral treatment or vaccine is available; however, multiple clinical trials are evaluating the safety and efficacy of pharmacologic agents.

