### 8.4 Safety monitoring and stopping rule

This study will enroll the first 6 patients to the MSC arm for safety run in. Based on experience, we expect the toxicity of MSC is low about 5-10%. The chance of observing tSAEs in more than two out of six patients is 1.6%. After the first six patients complete safety monitoring at day 28, we will halt the study if more than two patients have tSAEs. Otherwise, the study will continue to enroll additional patients

The study will continuously monitor the safety of MSCs infusions in patients who are randomized to the MSC arm so that the accrual can be halted early if there is an unexpectedly high rate of treatment-related serious adverse events (tSAE) at day 28, defined in Section 7.4.5. Patients who don't complete the 28-day observation due to a reason other than tSAE will be deemed not evaluable for tSAE. However, those patients in the randomization phase are evaluable for efficacy and will not be replaced. A tSAE rate of greater than or equal to 25% is considered excessive. The occurrence of tSAEs will be monitored using a stopping guideline based on a Pocock-type boundary method [83]. The following sequential stopping boundaries will be used:

Number of Patients	1-3	4-5	6-7	8-9	10-12	13-14	15-17	18-20	21-23	24-26	27-28	29-30
Number of tSAEs <	-	4	5	6	7	8	9	10	11	12	13	14

The accrual will be halted if the number of tSAEs is equal to or exceeds the boundary in the above table. Under this sequential stopping rule, the probability of early stopping is 5% if the true tSAE rate is 25%, and the probability of early stopping will be high at 81% if the true tSAE rate is 50%.

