## **9.2 Off Study Criteria**

- 9.2.1.** Completion of all study specified procedures
- 9.2.2.** Refusal of further study follow-up by patient or legal guardian
- 9.2.3.** Lost to follow up
- 9.2.4.** Death

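### Section 7.4.5 contradicts itself on the primary safety endpoint: its lead-in requires relatedness to MSCs, but its list counts every death and every lasting grade 4 event

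*Combined protocol and SAP*

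**What the plan says.** Section 7.4.5 opens with a relatedness test: "Treatment-related serious adverse events (tSAE) will be considered as those directly related to the investigational infusion product". It asks that alternative causes be weighed, naming COVID-19 itself, together with the timing of the event.

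The operative definition follows: "The safety endpoint of the study is tSAE, defined as", and then five items:

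1. Every grade 5 adverse event.
2. "Any grade 4 AE that fails to return to grade 2 within 72 hours post-infusion".
3. Allergic reactions of grade 2 to 4.
4. Thromboembolism within 48 hours of infusion.
5. A serious adverse event (SAE) that, in the treating physician's judgement, "is considered related to MSC infusion and requires withdrawal from the study".

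Only item 5 restates relatedness.

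Section 8.4 builds two halting rules on this endpoint. The run-in halts if more than two of six patients have a tSAE. A Pocock-type boundary then runs over the 30 patients randomized to MSCs. The planning statement is "Based on experience, we expect the toxicity of MSC is low about 5-10" percent, and a rate of 25% or more is called excessive. tSAEs are monitored to day 28.

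On background risk, section 1.3 describes COVID-19 ARDS "with mortality approaching 50% in various studies". Section 9.2 gives four ways off study: "Completion of all study specified procedures", refusal of further follow-up, loss to follow-up, and death.

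**The concern.** tSAE is the primary safety endpoint and the only trigger of both halting rules, so its definition has to be unambiguous. As written, a COVID-19 death in an infused patient is not a tSAE under the lead-in and is one under item 1. The wording invites the literal reading: if the lead-in governed every item, there would be no need to restate relatedness in item 5.

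The reading also changes the denominator. Section 8.4 makes a patient who does not complete 28 days for a reason other than a tSAE not evaluable. Under the related reading, a patient who dies of COVID-19 before day 28 drops out of the tSAE count. Under the literal reading the same patient is an event. Identical data could therefore halt the trial or let it continue.

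**Working it through.** **Inputs.** From section 8.4: the run-in rule (halt at 3 or more of 6), the expected rate of 5-10%, the excessive rate of 25%, and the boundary. The boundary halts when the tSAE count reaches 4 at 4-5 patients, 5 at 6-7, 6 at 8-9, 7 at 10-12, 8 at 13-14, 9 at 15-17, 10 at 18-20, 11 at 21-23, 12 at 24-26, 13 at 27-28 and 14 at 29-30. From section 1.3: mortality near 50%. The 28-day mortality of this trial's population is not given, so 20-50% is an assumed range.

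**Formulas.**
- Run-in: R(p) = 1 − Σ C(6,k) p^k (1−p)^(6−k), for k = 0 to 2.
- Boundary: with P_n(x) the probability of x events after n patients without a halt, P_n(x) = (1−p)·P_(n−1)(x) + p·P_(n−1)(x−1). Probability at or above the boundary is added to S(p) and removed at each n, up to n = 30. The count starts at zero with the first randomized MSC patient.
- Either rule: R + (1 − R)·S.

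**The plan's own figures.** At p = 0.10, R = 1 − (0.5314 + 0.3543 + 0.0984) = 0.0159, the stated 1.6%. At 5% it would be 0.2%, so the stated figure belongs to the upper end of 5-10%. The boundary gives S = 0.0489 at 25% (stated 5%) and 0.8127 at 50% (stated 81%). All three reproduce.

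**The two readings.** The literal rows take a harmless product and count deaths only.

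| Reading | Event rate | Run-in halts | Boundary halts | Either |
|---|---|---|---|---|
| Related events | 10% | 1.6% | 0.06% | 1.6% |
| Literal, deaths | 20% | 9.9% | 1.5% | 11% |
| Literal, deaths | 25% | 16.9% | 4.9% | 21% |
| Literal, deaths | 30% | 25.6% | 12.6% | 35% |
| Literal, deaths | 40% | 45.6% | 44.9% | 70% |
| Literal, deaths | 50% | 65.6% | 81.3% | 94% |

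For example, at 40%: 0.4557 + 0.5443 × 0.4491 = 0.700. Lasting grade 4 events would raise the literal rows further, but the documents give no rate for them.

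**The 72-hour clock.** Item 2 counts from infusion, while monitoring runs to day 28. A grade 4 event that begins on day 4 cannot be back at grade 2 within 72 hours of infusion. It might therefore always count, or the item might cover only the first 72 hours. A second infusion, allowed by section 5.3.1, adds the question of which infusion starts the clock.

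**The withdrawal condition.** Item 5 needs both relatedness and withdrawal from the study. None of the four routes in section 9.2 is withdrawal for an adverse event, and section 9.1 concerns coming off treatment only. A related grade 3 SAE that is neither a listed allergic reaction nor an early thromboembolic event meets none of items 1-4 and may have no route into item 5.

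**The case against.** The strongest reply is that the lead-in controls. It comes first, requires direct relatedness and names COVID-19 as an alternative cause. The endpoint is called treatment-related throughout, and the 5-10% planning rate is described as MSC toxicity. This stands as evidence of intent: a reader might infer that the two readings have equal support, and they do not. It does not remove the conflict, because the sentence that defines the endpoint introduces items that drop the condition.

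A reader might also infer that any related SAE counts only if the patient is withdrawn. That goes too far. Related deaths, lasting grade 4 events, listed allergic reactions and early thromboembolism count without withdrawal, so the gap is confined to other related SAEs. Those are not lost from the record either: section 8.5 tabulates all adverse events, grades and attributions by arm. They are lost only from the primary endpoint and the halting rules.

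Nor do the documents support saying that neither reading measures MSC safety. The related reading does measure product harm, though incompletely and by unblinded judgement.

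Finally, the large halting probabilities depend on mortality. At 20-30% the chance of a halt is 11-35%, and ventilation is not an entry requirement. It would be wrong to say that the trial would probably halt without stating the mortality assumed.

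**Conclusion.** The concern holds as an internal contradiction in the primary safety endpoint, with two narrower gaps. The related reading is the one that section 8.4 supports, with an overall false-halt probability of about 1.6% at a 10% event rate. The definition applied as written gives 11% to 94% across the mortality range shown, for a product that does no harm. It needs correcting because it can produce a wrong halting decision and the correction is cheap.

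The figures assume independent patients, deaths within the 28-day window, all 6 and then 30 patients evaluable, and no tSAEs other than deaths in the literal rows. The 72-hour item is ambiguous; the text does not establish that every late grade 4 event counts.

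**What to change.** In section 7.4.5:

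- Reconcile the lead-in, the list and section 8.4 by stating that the lead-in's existing attribution standard governs the grade 5 and grade 4 items. Leave the standard itself unchanged. A looser threshold, such as possible relatedness, would be a different endpoint, and nothing shows that the 5-10% and 25% rates would still apply to it.
- Leave the time-based thromboembolism item as strong as it is. Section 1.6 identifies this risk, and an added unblinded relatedness judgement would weaken the item.
- State from when the 72 hours in the grade 4 item run, including after a second infusion.
- Reconcile the withdrawal condition in the last item with section 9.2, so that related SAEs are not dropped from the endpoint.

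Because attribution is made without blinding, show all-cause deaths and grade 4 events by arm beside the tSAE count at safety reviews. The monitoring plan cited in section 10 is not part of these documents and may already require this.

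The cost is a wording amendment and one table from data already collected. The small downside is that the reported tSAE rate may rise slightly once other related SAEs are counted.
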